5.3.3 Doxorubicin

For patients accrued on cohort 1: For dose adjustment see package insert for subjects receiving this agent, once the trial dose is selected. We will have a safety lead-in employing a 3-at-risk rolling design. For each treatment, we will permit only 3 patients to be a risk for first cycle toxicities at any one time during the safety-lead in. Dose escalation from 50mg/m² to 60mg/m² will be permitted according the 3-at-risk dose escalation rules (below). Once the safety lead-in is complete, accrual will proceed. Any dose de-escalation from 50mg/m² will require discussion with the sponsor and an amendment. DLTs are defined in section 8.1. below.

5.3.4 Aromatase inhibitors

Exemestane 25 mg daily po, anastrozole 1 mg po daily, or letrozole 2.5 mg po daily will be administered as per package insert. There will be no dose-adjustment for these agents.

5.3.5 Trial Blinding/Masking

This is an open-label trial; therefore, the Sponsor, investigator and subject will know the treatment administered.

5.4 Randomization or Treatment Allocation

Patients with triple negative stage 4 breast cancer will receive pembrolizumab and doxorubicin in cohort 1; patients with HR+ stage IV breast cancer will receive pembrolizumab and an aromatase inhibitor.

5.5 Stratification

Accrual will not depend on stratification, but for Cohort 1 we will consider stratified analysis based on first-line (for metastatic or newly diagnosed), versus lines 2 or beyond for metastatic disease.

5.6 Concomitant Medications/Vaccinations (allowed & prohibited)

Medications or vaccinations specifically prohibited in the exclusion criteria are not allowed during the ongoing trial. If there is a clinical indication for one of these or other medications or vaccinations specifically prohibited during the trial, discontinuation from trial therapy or vaccination may be required. The investigator should discuss any questions regarding this with the Merck Clinical team. The final decision on any supportive therapy or vaccination rests with the investigator and/or the subject's primary physician.

5.6.1 Acceptable Concomitant Medications

All treatments that the investigator considers necessary for a subject's welfare may be administered at the discretion of the investigator in keeping with the community standards of medical care. All concomitant medication will be recorded on the case report form (CRF) including all prescription, over-the-counter (OTC), herbal supplements, and IV medications and fluids. If changes occur during the trial period, documentation of drug dosage, frequency, route, and date may also be included on the CRF. Subjects who are taking a bisphosphonate or denosumab when they enter the study may continue to take the drug while on the study treatment.

All concomitant medications received within 28 days before the first dose of trial treatment and 30 days after the last dose of trial treatment should be recorded. Concomitant medications administered after 30 days after the last dose of trial treatment should be recorded for SAEs and ECIs as defined in Section 7.2.

5.6.2 Prohibited Concomitant Medications

Subjects are prohibited from receiving the following therapies during the Screening and Treatment Phase (including retreatment for post-complete response relapse) of this trial:

Antineoplastic systemic chemotherapy or biological therapy
 Immunotherapy not specified in this protocol
 Chemotherapy not specified in this protocol
 Investigational agents other than pembrolizumab
 Radiation therapy

Note: Radiation therapy to a symptomatic solitary lesion or to the brain may be allowed at the investigator's discretion.

- Live vaccines within 30 days prior to the first dose of trial treatment and while participating in the trial. Examples of live vaccines include, but are not limited to, the following: measles, mumps, rubella, varicella/zoster, yellow fever, rabies, BCG, and typhoid vaccine.

Systemic glucocorticoids for any purpose other than to modulate symptoms from an event of clinical interest of suspected immunologic etiology. The use of physiological doses of corticosteroids (≤ 10 mg prednisone or equivalent po daily) is allowed.

Subjects who, in the assessment by the investigator, require the use of any of the aforementioned treatments for clinical management should be removed from the trial. Subjects may receive other medications that the investigator deems to be medically necessary.

The Exclusion Criteria describes other medications which are prohibited in this trial.

There are no prohibited therapies during the Post-Treatment Follow-up Phase.

5.7 Rescue Medications & Supportive Care

5.7.1 Supportive Care Guidelines

Subjects should receive appropriate supportive care measures as deemed necessary by the treating investigator. Suggested supportive care measures for the management of adverse events with potential immunologic etiology are outlined below and in greater detail in the ECI guidance document. Where appropriate, these guidelines include the use of oral or intravenous treatment with corticosteroids as well as additional anti-inflammatory agents if symptoms do not improve with administration of corticosteroids. Note that several courses of steroid tapering may be necessary as symptoms may worsen when the steroid dose is

decreased. For each disorder, attempts should be made to rule out other causes such as metastatic disease or bacterial or viral infection, which might require additional supportive care. The treatment guidelines are intended to be applied when the investigator determines the events to be related to pembrolizumab.

Note: if after the evaluation the event is determined not to be related, the investigator is instructed to follow the ECI reporting guidance but does not need to follow the treatment guidance (as outlined in the ECI guidance document). Refer to Section 5.2.1 for dose modification.

It may be necessary to perform conditional procedures such as bronchoscopy, endoscopy, or skin photography as part of evaluation of the event. Suggested conditional procedures, as appropriate, can be found in the ECI guidance document.

- **Pneumonitis:**

- For **Grade 2 events**, treat with systemic corticosteroids. When symptoms improve to Grade 1 or less, steroid taper should be started and continued over no less than 4 weeks.
- For **Grade 3-4 events**, immediately treat with intravenous steroids. Administer additional anti-inflammatory measures, as needed.
- Add prophylactic antibiotics for opportunistic infections in the case of prolonged steroid administration.

- **Diarrhea/Colitis:**

Subjects should be carefully monitored for signs and symptoms of enterocolitis (such as diarrhea, abdominal pain, blood or mucus in stool, with or without fever) and of bowel perforation (such as peritoneal signs and ileus).

- All subjects who experience diarrhea/colitis should be advised to drink liberal quantities of clear fluids. If sufficient oral fluid intake is not feasible, fluid and electrolytes should be substituted via IV infusion. For Grade 2 or higher diarrhea, consider GI consultation and endoscopy to confirm or rule out colitis.
- For **Grade 2 diarrhea/colitis** that persists greater than 3 days, administer oral corticosteroids.
- For **Grade 3 or 4 diarrhea/colitis** that persists > 1 week, treat with intravenous steroids followed by high dose oral steroids.
- When symptoms improve to Grade 1 or less, steroid taper should be started and continued over no less than 4 weeks.

- **Type 1 diabetes mellitus (if new onset, including diabetic ketoacidosis [DKA]) or \geq Grade 3 Hyperglycemia, if associated with ketosis (ketonuria) or metabolic acidosis (DKA)**

- For **T1DM** or **Grade 3-4** Hyperglycemia
 - Insulin replacement therapy is recommended for Type I diabetes mellitus and for Grade 3-4 hyperglycemia associated with metabolic acidosis or ketonuria.
 - Evaluate patients with serum glucose and a metabolic panel, urine ketones, glycosylated hemoglobin, and C-peptide.
- **Hypophysitis:**
 - For **Grade 2** events, treat with corticosteroids. When symptoms improve to Grade 1 or less, steroid taper should be started and continued over no less than 4 weeks. Replacement of appropriate hormones may be required as the steroid dose is tapered.
 - For **Grade 3-4** events, treat with an initial dose of IV corticosteroids followed by oral corticosteroids. When symptoms improve to Grade 1 or less, steroid taper should be started and continued over no less than 4 weeks. Replacement of appropriate hormones may be required as the steroid dose is tapered.
- **Hyperthyroidism or Hypothyroidism:**

Thyroid disorders can occur at any time during treatment. Monitor patients for changes in thyroid function (at the start of treatment, periodically during treatment, and as indicated based on clinical evaluation) and for clinical signs and symptoms of thyroid disorders.

 - **Grade 2** hyperthyroidism events (and **Grade 3-4** hypothyroidism):
 - In hyperthyroidism, non-selective beta-blockers (e.g. propranolol) are suggested as initial therapy.
 - In hypothyroidism, thyroid hormone replacement therapy, with levothyroxine or liothyroinine, is indicated per standard of care.
 - **Grade 3-4** hyperthyroidism
 - Treat with an initial dose of IV corticosteroid followed by oral corticosteroids. When symptoms improve to Grade 1 or less, steroid taper should be started and continued over no less than 4 weeks. Replacement of appropriate hormones may be required as the steroid dose is tapered.
- **Hepatic:**
 - For **Grade 2** events, monitor liver function tests more frequently until returned to baseline values (consider weekly).
 - Treat with IV or oral corticosteroids
 - For **Grade 3-4** events, treat with intravenous corticosteroids for 24 to 48 hours.
 - When symptoms improve to Grade 1 or less, a steroid taper should be started and continued over no less than 4 weeks.

- **Renal Failure or Nephritis:**
 - For **Grade 2** events, treat with corticosteroids.
 - For **Grade 3-4** events, treat with systemic corticosteroids.
 - When symptoms improve to Grade 1 or less, steroid taper should be started and continued over no less than 4 weeks.
- **Management of Infusion Reactions:** Signs and symptoms usually develop during or shortly after drug infusion and generally resolve completely within 24 hours of completion of infusion.

Table

Table 4 below shows treatment guidelines for subjects who experience an infusion reaction associated with administration of pembrolizumab (MK-3475).

Table 4 Infusion Reaction Treatment Guidelines

NCI CTCAE Grade	Treatment	Premedication at subsequent dosing
Grade 1 Mild reaction; infusion interruption not indicated; intervention not indicated	Increase monitoring of vital signs as medically indicated until the subject is deemed medically stable in the opinion of the investigator.	None
Grade 2 Requires infusion interruption but responds promptly to symptomatic treatment (e.g., antihistamines, NSAIDS, narcotics, IV fluids); prophylactic medications indicated for <=24 hrs.	
Stop Infusion and monitor symptoms. Additional appropriate medical therapy may include but is not limited to:
 
 IV fluids Antihistamines NSAIDS Acetaminophen Narcotics 
Increase monitoring of vital signs as medically indicated until the subject is deemed medically stable in the opinion of the investigator. If symptoms resolve within one hour of stopping drug infusion, the infusion may be restarted at 50% of the original infusion rate (e.g., from 100 mL/hr to 50 mL/hr). Otherwise dosing will be held until symptoms resolve and the subject should be premedicated for the next scheduled dose.
 
Subjects who develop Grade 2 toxicity despite adequate premedication should be permanently discontinued from further trial treatment administration.
	
Subject may be premedicated 1.5h (\pm 30 minutes) prior to infusion of pembrolizumab (MK-3475) with:
 
Diphenhydramine 50 mg po (or equivalent dose of antihistamine).
 
Acetaminophen 500-1000 mg po (or equivalent dose of antipyretic).

Grades 3 or 4 Grade 3: Prolonged (i.e., not rapidly responsive to symptomatic medication and/or brief interruption of infusion); recurrence of symptoms following initial improvement; hospitalization indicated for other clinical sequelae	
Stop Infusion. Additional appropriate medical therapy may include but is not limited to:
 
 IV fluids Antihistamines NSAIDS Acetaminophen Narcotics Oxygen Pressors 	No subsequent dosing

NCI CTCAE Grade	Treatment	Premedication at subsequent dosing
(e.g., renal impairment, pulmonary infiltrates) Grade 4: Life-threatening; pressor or ventilatory support indicated	Corticosteroids Epinephrine Increase monitoring of vital signs as medically indicated until the subject is deemed medically stable in the opinion of the investigator. Hospitalization may be indicated. Subject is permanently discontinued from further trial treatment administration.	
Appropriate resuscitation equipment should be available in the room and a physician readily available during the period of drug administration.		

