7.2.14 Evaluating Adverse Events

An investigator who is a qualified physician will evaluate all adverse events according to the NCI Common Terminology for Adverse Events (CTCAE), version 4.0. Any adverse event which changes CTCAE grade over the course of a given episode will have each change of grade recorded on the adverse event case report forms/worksheets.

All adverse events regardless of CTCAE grade must also be evaluated for seriousness.

Table 6 Evaluating Adverse Events

An investigator who is a qualified physician, will evaluate all adverse events as to:

V4.0 CTCAE Grading	Grade 1	Mild; asymptomatic or mild symptoms; clinical or diagnostic observations only; intervention not indicated.
	Grade 2	Moderate; minimal, local or noninvasive intervention indicated; limiting age-appropriate instrumental ADL.
	Grade 3	Severe or medically significant but not immediately life-threatening; hospitalization or prolongation or hospitalization indicated; disabling; limiting self-care ADL.
	Grade 4	Life threatening consequences; urgent intervention indicated.
	Grade 5	Death related to AE
Seriousness	A serious adverse event is any adverse event occurring at any dose or during any use of Merck product that:	
	†Results in death; or	
	†Is life threatening; or places the subject, in the view of the investigator, at immediate risk of death from the event as it occurred (Note: This does not include an adverse event that, had it occurred in a more severe form, might have caused death.); or	
	†Results in a persistent or significant disability/incapacity (substantial disruption of one's ability to conduct normal life functions); or	
	†Results in or prolongs an existing inpatient hospitalization (hospitalization is defined as an inpatient admission, regardless of length of stay, even if the hospitalization is a precautionary measure for continued observation. (Note: Hospitalization [including hospitalization for an elective procedure] for a preexisting condition which has not worsened does not constitute a serious adverse event.); or	
	†Is a congenital anomaly/birth defect (in offspring of subject taking the product regardless of time to diagnosis); or	
	Is a new cancer; (that is not a condition of the study) or	

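### Section 5.7.1 sets a later steroid trigger for Grade 3 or 4 diarrhea/colitis (more than 1 week) than for Grade 2 (more than 3 days)

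*Combined protocol and SAP*

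**What the plan says.** The diarrhea/colitis part of section 5.7.1 (Supportive Care Guidelines) has two adjacent bullets on steroids:

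- Grade 2: an event "that persists greater than 3 days, administer oral corticosteroids".
- Grade 3 or 4: an event "that persists > 1 week, treat with intravenous steroids followed by high dose oral steroids".

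The same part asks for monitoring for enterocolitis and bowel perforation, for fluids, and for GI consultation and endoscopy to be considered from Grade 2. None of these depends on how long the event has lasted.

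The opening of 5.7.1 describes the measures as suggested, leaves supportive care to the treating investigator, applies the guidelines to events judged related to pembrolizumab, and refers to an ECI guidance document for more detail. Table 3 in section 5.3.1.2 deals separately with pembrolizumab: hold for Grade 2-3 diarrhea/colitis, stop permanently at Grade 4. Section 5.6.2 allows systemic steroids for suspected immune-related events and sets no minimum duration.

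**The concern.** A treatment trigger should come no later as the event becomes more serious. Here it comes later. An investigator who follows the two bullets literally would start steroids for moderate colitis after 3 days but wait beyond 7 days for severe or life-threatening colitis. The 3-day step is written for Grade 2 only, so it does not cover Grade 3 or 4 in the meantime.

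What is at stake is the timing of the specific treatment for a pembrolizumab toxicity whose danger the protocol itself recognizes through its instruction to watch for perforation. The point concerns patient safety and the clarity of the instruction. It does not bear on the statistical design.

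**Working it through.** The plan gives no calculated figure to reproduce. The check is a comparison of texts with one subtraction and one count.

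**1. The two thresholds (section 5.7.1, diarrhea/colitis)**

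| Grade | Persistence before steroids | Suggested steroid |
|---|---|---|
| 2 | more than 3 days | oral |
| 3 or 4 | more than 1 week = 7 days | intravenous, then high-dose oral |

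Difference between thresholds: 7 − 3 = 4 days. Ratio: 7 / 3 = 2.3. Both are lower bounds on a waiting time, so these figures compare the written triggers and do not predict actual start times.

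As an illustration, take two patients whose related diarrhea starts on the same day and does not settle, one at Grade 2 and one at Grade 3. From just after day 3 until day 7 the text suggests steroids for the Grade 2 patient and not yet for the Grade 3 patient.

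**2. The other immune-related events in 5.7.1 with a steroid instruction at Grade 3-4**

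| Event | Grade 3-4 instruction | Waiting period |
|---|---|---|
| Pneumonitis | "immediately treat with intravenous steroids" | none (immediate) |
| Hypophysitis | "events, treat with an initial dose of IV corticosteroids followed by oral corticosteroids" | none stated |
| Hyperthyroidism | "Treat with an initial dose of IV corticosteroid followed by oral corticosteroids" | none stated |
| Hepatic | "treat with intravenous corticosteroids for 24 to 48 hours" | none stated |
| Renal failure or nephritis | "events, treat with systemic corticosteroids" | none stated |
| Diarrhea/colitis | as in step 1 | more than 1 week |

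Count: 6 events, of which 5 have no waiting period and 1 has one. Type 1 diabetes/hyperglycemia (managed with insulin), hypothyroidism (hormone replacement) and infusion reactions (covered by Table 4) are outside this count.

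**3. Is there an earlier start for Grade 3 or 4 elsewhere in the document?**

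- Table 3 (section 5.3.1.2) covers holding or stopping pembrolizumab and how long a steroid taper may take. It gives no time for starting steroids.
- Section 5.6.2 permits steroids but does not say when to begin them.
- Section 8.1.2 exempts Grade 3 diarrhea from counting as a DLT only if medical intervention controls it within 72 hours. That is not a steroid trigger. It does show that the protocol elsewhere uses 3 days, not 7, as the limit for uncontrolled severe diarrhea.
- Table 6 (section 7.2.14) describes Grade 4 as "Life threatening consequences; urgent intervention indicated". It names no treatment, but a wait of more than a week for the suggested drug therapy fits poorly with it.

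None of these places corrects the trigger.

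**The case against.** The strongest reply is that the bullet neither requires the delay nor forbids earlier treatment. The measures are suggestions, care is left to the investigator's judgment, and section 5.6.2 would allow steroids on the first day of a Grade 3 or 4 event. Monitoring, fluids, consideration of endoscopy and the Table 3 hold or discontinuation all apply without a wait. The ECI guidance document, to which the protocol sends investigators for management, was not among the texts reviewed and may set an earlier trigger. All of this stands and limits the likely harm. It does not make the written order right. If the guidance document starts steroids sooner, the protocol disagrees with it; if it repeats the week, both need correcting.

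Other points stand in part:

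- Of the five comparison events, only pneumonitis says to treat at once; the other four simply state no start time. Diarrhea/colitis is also the only one with a persistence condition at Grade 2. A persistence condition is therefore not an error in itself. The anomaly is the order of the two grades.
- The Grade 4 definition is a general grading scale that could be met by other interventions, and Table 3 concerns pembrolizumab rather than steroids. Both are supporting evidence only.
- The wait might be meant to let infection be ruled out, or to gate only the step up to intravenous treatment. The first would not explain a longer wait at the higher grades. The second is not written anywhere for Grade 3 or 4.
- No document reviewed establishes prompt intravenous steroids as the standard for every related Grade 3 colitis. This is why the fix includes a fallback and a check against the guidance document.

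**Conclusion.** The concern holds. As written, the suggested steroid trigger for diarrhea/colitis is inverted by severity: the Grade 3 or 4 threshold is 4 days later than the Grade 2 threshold, and this is the only waiting period among the six Grade 3-4 steroid instructions in 5.7.1. The sponsor should correct it.

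The reading of the text is certain. The practical effect is less so, because it depends on how literally sites follow a suggestion and on what the ECI guidance document says. The documents give no rate of Grade 3 or 4 colitis, so the number of patients affected cannot be estimated. No effect on endpoints, sample size, error rates or the DLT rules is claimed.

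**What to change.** Remove the one-week persistence condition from the Grade 3 or 4 diarrhea/colitis bullet in section 5.7.1, so that intravenous steroids start promptly once the event is judged related to pembrolizumab. If the sponsor wishes to keep a persistence condition, set it no later than the 3 days used for Grade 2. Before finalizing the wording, compare it with the ECI guidance document so that both give the same trigger.

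The change affects one bullet. Its clinical cost is that some patients whose diarrhea would have settled without steroids will receive them, followed by the taper of at least 4 weeks that 5.7.1 already requires. Restricting the guideline to events judged pembrolizumab-related, as it is now, limits that cost.

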5.8 Diet/Activity/Other Considerations

5.8.1 Diet

Subjects should maintain a normal diet unless modifications are required to manage an AE such as diarrhea, nausea or vomiting.

5.8.2 Contraception

Pembrolizumab may have adverse effects on a fetus in utero. Furthermore, it is not known if pembrolizumab has transient adverse effects on the composition of sperm. Non-pregnant, non-breast-feeding women may be enrolled if they are willing to use 2 methods of birth control or are considered highly unlikely to conceive. Highly unlikely to conceive is defined as 1) surgically sterilized, or 2) postmenopausal (a woman who is ≥ 45 years of age and has not had menses for greater than 1 year will be considered postmenopausal), or 3) not heterosexually active for the duration of the study. The two birth control methods can be either two barrier methods or a barrier method plus a hormonal method to prevent pregnancy. Subjects should start using birth control from study Visit 1 throughout the study period up to 120 days after the last dose of study therapy.

The following are considered adequate barrier methods of contraception: diaphragm, condom (by the partner), copper intrauterine device, sponge, or spermicide. Appropriate hormonal contraceptives will include any registered and marketed contraceptive agent that contains an estrogen and/or a progestational agent (including oral, subcutaneous, intrauterine, or intramuscular agents).

Subjects should be informed that taking the study medication may involve unknown risks to the fetus (unborn baby) if pregnancy were to occur during the study. In order to participate in the study they must adhere to the contraception requirement (described above) for the duration of the study and during the follow-up period defined in section 7.2.2-Reporting of Pregnancy and Lactation to the Sponsor and to Merck. If there is any question that a subject will not reliably comply with the requirements for contraception, that subject should not be entered into the study.

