2.2 Trial Diagram

3.0 OBJECTIVE(S) & HYPOTHESIS(ES)

3.1 Primary Objective(s) & Hypothesis(es)

(1) Objective:

1.a To evaluate efficacy (overall response rate) of MK-3475 and doxorubicin in patients with stage IV triple negative breast cancer.

Hypothesis: Interference with breast cancer-associated PD-1 receptor expression will lead to increased cellular (CD8+) immunity. This effect is likely to occur regardless of tumor subtype (i.e. hormone receptor positive, HER2+, or triple negative subtypes), but targeting the PD-1 receptor alone may not provide sufficient therapeutic benefit. Preclinical and clinical data suggest that the prevalence of PD-1 and PD-L1 expression is highest among patients with triple negative primary disease. We postulate that if such is also true in the metastatic setting, a combination of MK-3475 and a DNA-targeting chemotherapeutic agent with the potential to interfere with the interaction of PD-1 and PD-L1/L2 such as doxorubicin may be of additive or even synergistic therapeutic value through facilitating both cellular immune response and chemotherapy effects.

(2) Objective:

To evaluate efficacy (overall response rate) of MK-3475 and an oral aromatase inhibitor in patients with stage IV HR+ HER2- breast cancer.

Hypothesis: The combination of MK-3475, and antiestrogen therapy will provide a novel treatment option for primarily endocrine therapy-resistant patients through enhancing cellular immune response while preserving the anti-estrogen effect. Current practice calls for initiating cytotoxic therapy once the first few lines of anti-estrogen treatment options have been exhausted. We postulate that MK-3475, when given together with whichever aromatase inhibitor has not been administered to a patient previously, may provide a less toxic and potentially better therapeutic option.

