International Normalized Ratio (INR) or Prothrombin Time (PT)	$\leq 1.5 \times$ ULN unless subject is receiving anticoagulant therapy as long as PT or PTT is within therapeutic range of intended use of anticoagulants
Activated Partial Thromboplastin Time (aPTT)	$\leq 1.5 \times$ ULN unless subject is receiving anticoagulant therapy as long as PT or PTT is within therapeutic range of intended use of anticoagulants
Reproductive status for cohort 2: HR+ stage IV post-menopausal breast cancer	
Post-menopausal is defined by at least one of the following criteria:
 
Prior bilateral oophorectomy OR Amenorrheic for ≥ 12 months (if ≤ 55 years of age and prior chemotherapy or on medical ovarian ablative therapy or received ovarian radiation for ablation in the past 5 years and/or tamoxifen or an AI within the past year, then FSH and estradiol must be in the post-menopausal range and obtained within 28 days prior to registration) OR
 
Previous hysterectomy with one or both ovaries left in place (or previous hysterectomy in which documentation of bilateral oophorectomy is unavailable AND FSH values consistent with the institutional normal values for the post-menopausal state. FSH levels must be obtained within 28 days prior to registration).

^aCreatinine clearance should be calculated per institutional standard. [#] For patients with triple negative breast cancer [^] For patient with HR+ breast cancer
	

7. Female subject of childbearing potential should have a negative urine or serum pregnancy within 72 hours prior to receiving the first dose of study medication. If the urine test is positive or cannot be confirmed as negative, a serum pregnancy test will be required.
8. Female subjects of childbearing potential should be willing to use 2 methods of birth control or be surgically sterile, or abstain from heterosexual activity for the course of the study through 120 days after the last dose of study medication (Reference Section 5.7.2). Subjects of childbearing potential are those who have not been surgically sterilized or have not been free from menses for > 1 year.
9. Male subjects should agree to use an adequate method of contraception starting with the first dose of study therapy through 120 days after the last dose of study therapy.

10. Subjects currently on a bisphosphonate or denosumab are eligible for study therapy.

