5.1.2 Subject Exclusion Criteria

The subject must be excluded from participating in the trial if the subject:

1. Cohort 1: Has triple negative breast cancer, is considered for cohort 1 participation, and received prior anthracycline therapy.
Cohort 2: Has received prior aromatase inhibitor therapy and is deemed to be resistant to all three (anastrozole, letrozole, exemestane) approved AIs. Resistance is defined as progression within 12 months or while on an AI.
2. Patient is premenopausal (see Table 1, medical ovarian suppression is allowed)Is currently participating and receiving study therapy or has participated in a study of an investigational agent and received study therapy or used an investigational device within 4 weeks of the first dose of treatment.
3. Has a diagnosis of immunodeficiency or is receiving systemic steroid therapy or any other form of immunosuppressive therapy within 7 days prior to the first dose of trial treatment.
4. Has a known history of active TB (Bacillus Tuberculosis)
5. Hypersensitivity to pembrolizumab or any of its excipients.
6. Suboptimal cardiac function as defined by decreased left ventricular ejection fraction < 55% for cohort 1, and < 50% for cohort 2.
7. Prior pembrolizumab.
8. Has had a prior anti-cancer monoclonal antibody (mAb) within 4 weeks prior to study Day 1 or who has not recovered (i.e., \leq Grade 1 or at baseline) from adverse events due to agents administered more than 4 weeks earlier.
9. Has had prior chemotherapy, targeted small molecule therapy, or radiation therapy within 2 weeks prior to study Day 1 or who has not recovered (i.e., \leq Grade 1 or at baseline) from adverse events due to a previously administered agent.
 - Note: Subjects with \leq Grade 2 neuropathy are an exception to this criterion and may qualify for the study.

- Note: If subject received major surgery, they must have recovered adequately from the toxicity and/or complications from the intervention prior to starting therapy.

10. Has a known additional malignancy that has progressed or required active treatment in the past 5 years. Exceptions include basal cell carcinoma of the skin or squamous cell carcinoma of the skin that has undergone potentially curative therapy or in situ cervical cancer.

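### Section 5.8.2 accepts estrogen-containing contraceptives trial-wide and makes no exception for Cohort 2 women taking an aromatase inhibitor; a minor patient-protection gap of very small, possibly zero, reach

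*Combined protocol and SAP*

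**What the plan says.** Section 5.8.2 covers the whole trial and names no cohort. A woman may enrol if she will use two contraceptive methods or falls into a group regarded as very unlikely to become pregnant. On the choice of methods it says: "The two birth control methods can be either two barrier methods or a barrier method plus a hormonal method to prevent pregnancy". Acceptable hormonal products include "any registered and marketed contraceptive agent that contains an estrogen and/or a progestational agent". The very-unlikely group is given by a definition with three branches: surgical sterility, postmenopausal status, or no heterosexual activity. The postmenopausal branch sets a lower age limit, which from the number onward reads "45 years of age and has not had menses for greater than 1 year will be considered postmenopausal". The section also makes adherence to its requirement a condition of taking part.

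For Cohort 2, section 5.4 states that "patients with HR+ stage IV breast cancer will receive pembrolizumab and an aromatase inhibitor". The hypothesis under objective (2) in section 3.1 expects benefit through "enhancing cellular immune response while preserving the anti-estrogen effect". Exclusion 2 bars premenopausal patients but adds that "medical ovarian suppression is allowed". Table 1 in section 5.1.1 defines post-menopausal by oophorectomy, by at least 12 months of amenorrhea, or by hysterectomy with supporting evidence. Under the amenorrhea route, for women aged 55 or younger with certain histories, including current ovarian ablative therapy, "then FSH and estradiol must be in the post-menopausal range and obtained within 28 days prior to registration".

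**The concern.** The study drug in Cohort 2 is described in the protocol's own summary as anti-estrogen therapy, and Table 1 asks for a post-menopausal estradiol level in some of these women before they register. A rule that lists an estrogen-containing product as suitable, without excepting this cohort, runs against both. At stake is the protection of an individual patient with HR+ metastatic disease: the contraception text, taken alone, would raise no objection to her using estrogen alongside her AI. Neither the flow chart in section 6.1 nor Table 5 includes estradiol, so no scheduled test during treatment would bring it to light.

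**Working it through.** No arithmetic applies. The check is whether any Cohort 2 woman is both eligible and still subject to the contraception rule, and whether any other section supplies the missing exception.

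**Step 1: who enters Cohort 2.** Table 1 offers three routes. Women with bilateral oophorectomy or hysterectomy are surgically sterile, so 5.8.2 asks nothing of them. The amenorrhea route needs at least 12 months without menses and has no lower age limit.

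**Step 2: who needs contraception.** Two texts answer this differently.

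| Text | Women exempt through absence of menses |
|---|---|
| Inclusion 8, evident sense | No menses for more than 1 year, at any age |
| Section 5.8.2 | No menses for more than 1 year **and** aged 45 or over |

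Inclusion 8 is loosely drafted. Its literal wording would place every unsterilized woman in the childbearing group whatever her age, which cannot be meant.

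**Step 3: a hypothetical case.** Take a woman aged 40 on ovarian suppression, 18 months without menses, with FSH and estradiol in the post-menopausal range, unsterilized and heterosexually active.

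- Table 1: 18 ≥ 12 months; 40 ≤ 55, so the hormone tests apply, and she passes them. She is eligible.
- Inclusion 8, evident sense: 18 months is more than 1 year, so no contraception is required.
- Section 5.8.2: 40 < 45, so she is outside the postmenopausal branch, and the other two branches do not fit. Two methods are required, one of which may be hormonal, and an estrogen-containing product is on the accepted list.

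She is therefore exempt under one text and covered by the other.

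**Step 4: is there an exception elsewhere?** Section 5.6.2 does not list estrogens or hormonal contraceptives among prohibited therapies. Inclusion 8 and the retreatment criteria in 7.1.4.5 repeat the two-method rule without separating the cohorts. Section 5.3.4 has AIs given according to the package insert, and 7.1.1.8 has them prescribed by label and standard guidelines. Section 5.6.1 leaves concomitant treatment "at the discretion of the investigator in keeping with the community standards of medical care". Exclusion 15 lets the investigator keep out a patient whose other therapy could confound results or whose participation is not in her interest. None of these clauses mentions estrogen. What the inserts say cannot be seen from the documents.

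**The case against.** The strongest reply is that the group is empty. Every unsterilized Cohort 2 woman has gone at least 12 months without menses, and inclusion 8, an eligibility criterion on this very subject, evidently exempts women who have passed one year. The age clause in 5.8.2 might also be read as a sufficient condition for being postmenopausal, not a necessary one. The first argument stands in large part and is why the reach is very small. It does not close the gap: the age clause sits inside an explicit definition, and 5.8.2 makes compliance a condition of participation, so a careful site could apply it to a woman under 45.

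A second reply is that 5.8.2 concerns fetal risk, directs nobody to take estrogen, and leaves prescribing to the clauses on labels and community standards. This too is fair. A reader might infer that the protocol requires estrogen in Cohort 2. It does not: two barrier methods comply, as does a barrier with a progestational agent alone. A reader might also infer that a site could give estrogen while meeting every protocol requirement. That is not shown, because 5.3.4 and 7.1.1.8 bring in labelling that was not available for this review and might address the point. What survives is that a specific listing in the protocol points one way, and only general clauses or text outside it could point the other.

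**Conclusion.** The point holds as a minor correction for patient protection. Section 5.8.2 states a rule that is wrong for one cohort, and its own age threshold keeps that rule applicable to a small group of women whom Table 1 admits. This rests on reading the 5.8.2 definition as written; if inclusion 8 in its evident sense governs instead, the group is practically empty.

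No number can be put on the reach. The documents give no age distribution for Cohort 2, no share on ovarian suppression and no information on contraceptive choice, so any figure would consist of assumed shares. A reader might also infer a threat to the Cohort 2 efficacy conclusion (3 or more responses in 20 patients). Nothing in the documents supports that: the number of women affected may be zero, and no effect on the response-rate decision is claimed.

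**What to change.** Add one sentence to 5.8.2: for female Cohort 2 subjects, estrogen-containing contraceptives are not acceptable while the study aromatase inhibitor is being taken. Two barrier methods, which in the protocol's list include the copper IUD, remain available. Whether progestogen-only methods are acceptable is for the sponsor's physicians to decide. Limiting the sentence to female subjects leaves the partners of male patients unaffected.

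A matching line in 5.6.2 is optional. If added, it should cover only estrogen-containing contraceptives in Cohort 2, so that local estrogen for vaginal dryness, which sections 10.2 to 10.4 list as an AI side effect, stays a clinical decision. Reconciling the age limit in 5.8.2 with inclusion 8 would change who must use contraception and is a separate decision.

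The change needs no new data, visits or patients. Its downside is fewer contraceptive options for a few women. The consent pages were not available, so whether they need matching text could not be checked.
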